	
vital signs, and serum chemistry testing (if diuretics were discontinued or anti-hypertensive medications were adjusted) and final eligibility determination (utilizing telemedicine if a remote visit). Subjects who fail inclusion/exclusion criteria due to temporary or correctable reasons may be re-screened (up to 2 additional times after obtaining new informed consents) and after consultation with the medical monitor and sponsor. Immediately following successful completion of Visit 2, subjects will enter the Baseline Period.
 
Baseline Period (Visits 3 – 5): Following completion of all screening assessments and establishment of background medication stability, subjects will enter the 3-week no-study-drug Baseline Period during which time liver chemistry tests and serum creatinine (for eGFR calculation) will be assessed weekly to obtain baseline measurements and assess individual variability. Visits 3 and 4 may be conducted remotely by a HHC. After successful completion of Visit 5 assessments in the clinic, subjects will be dispensed study drug and begin treatment. This completes the Baseline Period and subjects will enter the Titration Period.
 
Titration Period (Visits 6 – 11): During a period of 3-6 weeks, the lixivaptan dose will be increased weekly according to the titration schedule to achieve a level that results in both a tolerable dose and reduced first morning (trough) spot urine specific gravity or until the maximum dose level (Level 4 [200 mg BID]) is reached. Dosing will be started at Level 1 (50 mg BID), but the minimum dose to enter the Maintenance Period is Level 2 (100 mg BID). In general, dose tolerability will be confirmed over an additional week of dosing before the subject advances to the Maintenance Period. At the 2 highest dose levels where aquaretic effects may be problematic in certain subjects, there will be an opportunity to reduce the evening (PM) dose (Level 3a [150 mg AM/100 mg PM] and Level 4a [200 mg AM/150 mg PM]). Liver chemistry tests will be assessed weekly throughout the Titration Period. Urine osmolality and specific gravity will be assessed at all titration visits that occur except Visit 11. All titration visits may be conducted remotely by a HHC with telemedicine.
 
Maintenance Period (Visits 12-24): Following successful completion of the Titration Period, subjects will continue to receive lixivaptan in the Maintenance Period at the dose level achieved at the end of the Titration Period for up to 52 weeks (12 months). In consultation with the medical monitor and sponsor, the Investigator has the option of reducing the dose to address potential hepatic and non-hepatic adverse events. Assessments, including liver chemistry tests, will be performed every 4 weeks during this period. Visits 12, 13, 14, 15, 16,

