Study Assessments:	
Subjects who tolerate their optimized dose will then enter the Maintenance Period during which they will continue at the lixivaptan dose level achieved at the end of the Titration Period. During the Maintenance Period, in consultation with the medical monitor and sponsor, the dose may be adjusted downward at the Investigator's discretion if needed to manage hepatic or non-hepatic side effects and may also be increased back to the dose achieved at the end of the Titration Period. The Investigator may temporarily hold the drug for up to 7 days, if necessary, to manage acute intercurrent illness, tolerability issues, planned or unplanned surgical procedures or life situations, e.g., airplane travel, etc. Additionally, subjects who have a longer interruption due to illness, including COVID-19, or other reasons may be able to re-start study drug when medically stable after discussion with the medical monitor and sponsor.
 
Safety: Liver chemistry tests (ALT, AST, total bilirubin, direct bilirubin, alkaline phosphatase), clinical laboratory (hematology, non-hepatic clinical chemistry, and urinalysis), 12-lead ECGs, vital signs, physical examination, adverse events (AEs), and serious adverse events (SAEs).
 
Efficacy: eGFR
 
Pharmacokinetic: Trough measurements of lixivaptan
 
Additional Investigations: DNA sample to assess genetic variants associated with hepatic abnormalities (if and when feasible). This is obtained under a biobanking informed consent at Visit 5 (or later).
							
Criteria for Evaluation:	
Primary Endpoint
 
Safety:
 
Proportion of subjects who develop ALT levels >3 x ULN during the Titration or Maintenance Periods that were assessed by the independent HERC to be at least probably related to lixivaptan and resulted in discontinuation of the study drug.
 
Secondary Endpoints
 
Safety:
 
Proportion of subjects who develop ALT levels >5 x ULN during the Titration or Maintenance Periods that were assessed by the independent HERC to be at least probably related to lixivaptan and resulted in discontinuation of the study drug.
 
Proportion of subjects who develop ALT levels >3 x ULN during the Titration or Maintenance Periods that were assessed by the independent HERC to be at least probably related to lixivaptan and resulted in dose reduction of the study drug.
							

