4.2.7 Withdrawals Due to Abnormal Liver Chemistry Test Results

Guidance for management of abnormal liver chemistry test results is provided in [Section 7.3.7](#). In some cases, it will be advisable to discontinue the study drug and under other circumstances dose reduction might be appropriate. These actions in response to abnormal liver chemistry test results must be discussed with the medical monitor and sponsor prior to taking any action (except in an emergency). If study drug is withdrawn, re-starting study drug should generally be encouraged after discussion with the medical monitor and sponsor, when liver chemistry tests have normalized or stabilized, and in conjunction with a plan for increased frequency of liver chemistry test monitoring. In certain circumstances described in [Section 7.3.7.2](#), restarting study drug should only occur when the HERC believes the relationship between the abnormal liver chemistry test results and the study drug is less than 50% according to the DILIN criteria, modified, [Section 13.2](#) (Fontana RJ 2009).¹⁸

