5.2 Dose Administered

During all treatment periods, study drug will be administered BID, with the PM dose administered approximately 10 hours after the AM dose. During the Lixivaptan Titration Period, lixivaptan will be started at Level 1 (50 mg BID) and will be increased weekly through Levels 2 (100 mg BID), 3 (150mg BID), and 4 (200 mg BID) according to the dosing schedule in Table 4. Two additional dose levels (Levels 3a and 4a) are provided that reduce the evening (PM) dose by 50 mg (from 150 mg to 100 mg and from 200 mg to 150 mg) if aquaretic effects are limiting subjects' tolerability at either the 150 mg BID or 200 mg BID dose levels, respectively. Titration will stop when a tolerable dose level is reached that achieves the goal of lowering trough (first AM) fasting spot urine specific gravity to ≤ 1.005 (as a point-of-care surrogate for U_{osm}) or the highest dose (Level 4 or 4a) is achieved (regardless of trough urine osmolality). Subjects tolerating the drug at Level 2, 3, and 3a, but not achieving the urine specific gravity goal may be allowed to continue in the study after consultation with the medical monitor and sponsor.

Table 4 Dosing Levels during the Lixivaptan Titration Period

Dose Level	AM Dose	PM Dose*
1 [†]	50 mg (1 capsule)	50 mg (1 capsule)
2	100 mg (2 capsules)	100 mg (2 capsules)
3	150 mg (3 capsules)	150 mg (3 capsules)
3a [‡]	150 mg (3 capsules)	100 mg (2 capsules)
4	200 mg (4 capsules)	200 mg (4 capsules)
4a [#]	200 mg (4 capsules)	150 mg (3 capsules)

*PM dose to be administered approximately 10 hours after the AM dose.

[†]Dose Level 1 is only for initiation of treatment.

[‡]Subjects having difficulty with aquaretic effects at Dose Level 3 can drop back to 150 mg in the AM and 100 mg in the PM (Dose Level 3a: 150/100 mg).

[#]Subjects having difficulty with aquaretic effects at Dose Level 4 can drop back to 200 mg in the AM and 150 mg in the PM (Dose Level 4a: 200/150 mg).

Once tolerability and reduced trough urine specific gravity are achieved (or tolerability and maximum dose), subjects will stay on that dose for 1 additional week to confirm tolerability (except when the dose is reduced to Level 3a or Level 4a after 2 weeks of dosing at Level 3

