or Level 4, respectively, when a single final week at the lower dose level is sufficient; see [Table 5](#)). The most common dosing scenarios that can be advanced to the Maintenance Period are shown in [Table 5](#). With concurrence of the medical monitor and the sponsor, some subjects may be allowed to enter the Maintenance Period at a lower dose (but not less than 100 mg BID) if tolerability is an issue after trying a higher dose (regardless of specific gravity result at the lower dose):

Table 5. Dosing Diagram in the Lixivaptan Titration Period

Dose Level	Week 1	Week 2	Week 3	Week 4	Week 5	Week 6
2	50 mg BID	100 mg BID	100 mg BID			
3	50 mg BID	100 mg BID	150 mg BID	150 mg BID		
3a	50 mg BID	100 mg BID	150 mg BID	150/100 mg (AM/PM)	150/100 mg (AM/PM)	
3a (when 2 nd week of Level 3 is not tolerated)	50 mg BID	100 mg BID	150 mg BID	150 mg BID	150/100 mg (AM/PM)	
4	50 mg BID	100 mg BID	150 mg BID	200 mg BID	200 mg BID	
4a	50 mg BID	100 mg BID	150 mg BID	200 mg BID	200/150 mg (AM/PM)	200/150 mg (AM/PM)
4a (when 2 nd week of Level 4 is not tolerated)	50 mg BID	100 mg BID	150 mg BID	200 mg BID	200 mg BID	200/150 mg (AM/PM)

Subjects will continue to adhere to the recommended fluid intake regimen outlined in [Section 5.8](#).

Subjects who tolerate their optimized dose will then enter the Maintenance Period during which time they will continue at the lixivaptan dose level achieved at the end of the Titration Period. During the Maintenance Period, the dose may be adjusted downward at the Investigator's discretion if needed to manage non-hepatic side effects and may also be increased back to the dose achieved at the end of the Titration Period. The Investigator may instruct the subject to hold the study drug for up to 7 days, if necessary, to manage acute intercurrent illness, tolerability issues, surgical procedures or life situations, e.g., airplane travel, etc. Additionally, subjects who have a longer interruption due to illness, including COVID-19, or other reasons may be able to re-start study drug when medically stable after discussion with the medical monitor and sponsor. Temporary or permanent study drug discontinuation for management of abnormal liver chemistry test results is described further in [Section 7.3.7](#).

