After the Investigator consults with the medical monitor and sponsor, temporary reduction in dose or interruption of study drug administration must be instituted if liver transaminase levels $>3 \times \text{ULN}$ or total bilirubin levels $>2 \times \text{ULN}$ are observed during the Titration or Maintenance Periods. All elevations meeting these thresholds will be assessed the HERC. In the case of study drug interruption, re-starting study drug should be encouraged (see [exception](#) below) after discussion with the medical monitor and sponsor, when liver chemistry tests have normalized or stabilized, and in conjunction with a plan for increased frequency of liver chemistry test monitoring.

In the presence of such liver chemistry test abnormalities, additional clinical testing (examples listed in Appendix 3 ([Section 13.3](#))) may be recommended by the medical monitor and sponsor and those results reported according to local guidelines.

Treatment with study drug cannot be resumed in subjects when:

- transaminase levels $>8 \times \text{ULN}$ at any time,
- transaminase levels $>5 \times \text{ULN}$ for more than 2 weeks, or
- concurrent elevations of transaminase levels $>3 \times \text{ULN}$ **and** total bilirubin $>2 \times \text{ULN}$

except under these circumstances:

Subjects with these levels of abnormality may be re-challenged with study drug if abnormalities were adjudicated as having a $\leq 50\%$ likelihood of being related to study drug (per DILI Network [DILIN] probability criteria, modified, [Section 13.2](#) (Fontana RJ 2009)¹⁸ by the HERC, and the Investigator, medical monitor, and sponsor agree to an intensive monitoring plan to mitigate risk. The subject must also be willing to comply with these monitoring measures, be informed of the potential risks, and consent to study drug re-challenge.

Liver chemistry test increases of a lesser extent should be discussed with the medical monitor. They may be related to the underlying variability of such tests in ADPKD patients. Generally, dosing should continue, but the frequency of laboratory testing should increase, particularly during the Maintenance Period. Slowing of titration may also be considered if the abnormalities occur during the Titration Period.

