Subjects who tolerate their optimized dose will then enter the Maintenance Period during which time they will continue at the lixivaptan dose level achieved at the end of the Titration Period. During the Maintenance Period, the dose may be adjusted downward at the Investigator's discretion if needed to manage non-hepatic side effects and may also be increased back to the dose achieved at the end of the Titration Period. The Investigator may instruct the subject to hold the study drug for up to 7 days, if necessary, to manage acute intercurrent illness, tolerability issues, surgical procedures or life situations, e.g., airplane travel, etc. Additionally, subjects who have a longer interruption due to illness, including COVID-19, or other reasons may be able to re-start study drug when medically stable after discussion with the medical monitor and sponsor. Temporary or permanent study drug discontinuation for management of abnormal liver chemistry test results is allowed.

A detailed description of procedures and assessments to be conducted during this study is summarized in the Scheduled of Study Assessments in Table 3.

Figure 2: Titration Flowchart

[figure not shown]

Table 3: Schedule of Procedures

		ening weeks)	Baseline (Weekly ± 3 days) (3 weeks)	Titration Period (Weekly ± 3 days) (Up to 6 weeks)						Maintenance Period (every 28 days ± 3 days) for 52 weeks		Follow-up Period (4 weeks after last dose ^b)
Visit Number	V1	V2 ^a	V3, 4, 5	V6	V7	V8	V9	V10	V11	V12-V23	V24	V25, 26, 27
Informed consent	Х											
Demographic information	Х											
Medical history/Prior meds	Х	Х										
Review eligibility (Inclusion/Exclusion)	Х	Х	V5									
ECG	Х		V5							V17	Х	V27
Vital signs ^c	Х	Х	Х	Х	Х	Х	Х	Х	Х	Х	Х	V27
Physical examination ^d	Х									V17	Х	V27
Body weight/height ^e	Х	Х	V5	Х	Х	Х	Х	Х	Х		Х	
Pregnancy test (WOCBP) ^f	Х		V5						Х	V14,17,20	Х	V27
Chemistry/Serology samples ^g												
Complete Chemistry Panel	Х	(X)	V5						Х	V14,17,20	Х	V27
Liver Chemistry Panel	Х	(X)	Х	Х	Х	Х	Х	Х	Х	Х	Х	V27
Serum Creatinine			V3, 4									V25, 26
HBsAg, Anti-HCV	Х											
Hematology ^h	Х		V5						Х	V17	Х	V27
Urinalysis	Х										Х	V27
Urine specific gravity/ osmolality ⁱ			V5	Х	Х	Х	Х	X			Х	V27
Trough PK sample ^j			V5						Х	(X)	(X)	
DNA sample ^k			V5									
Dosing review/Tolerability				Х	Х	Х	Х	Х	Х	Х		
Drug dispensation			V5	Х	Х	Х	Х	Х	Х	Х		
Drug reconciliation				Х	Х	Х	Х	Х	Х	Х	Х	
IRT entry	Х	Х	Х	Х	Х	Х	Х	Х	Х	Х	Х	Х
Adverse events ¹	<											>

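### Section 7.3.7.2 never requires lixivaptan to be stopped at its three severe liver levels: it bars only resumption and leaves dose reduction open with no upper limit

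*Protocol*

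**What the plan says.** Protocol Section 7.3.7.2 sets the dosing rule for liver test abnormalities in the Titration and Maintenance Periods. After consultation with the medical monitor and sponsor, "temporary reduction in dose or interruption of study drug administration must be instituted if liver transaminase levels" exceed 3 x ULN, or if total bilirubin exceeds 2 x ULN. The HERC assesses every elevation that meets these thresholds.

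The section then says "Treatment with study drug cannot be resumed in subjects when" any of three severe levels is reached:

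- transaminase above 8 x ULN at any time;
- transaminase above 5 x ULN for more than 2 weeks;
- transaminase above 3 x ULN concurrently with total bilirubin above 2 x ULN.

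Re-challenge after a severe level is permitted only if the HERC puts the likelihood of drug causation at 50% or less, an intensive monitoring plan is agreed, and the subject is informed of the risks and consents.

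Other sections bear on the same decision:

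- Protocol 4.2.7: "In some cases, it will be advisable to discontinue the study drug and under other circumstances dose reduction might be appropriate".
- Synopsis, Maintenance Period: "the Investigator has the option of reducing the dose to address potential hepatic and non-hepatic adverse events", in consultation with the medical monitor and sponsor.
- Synopsis, dosing text: the dose may be lowered to "manage hepatic or non-hepatic side effects and may also be increased back to the dose achieved at the end of the Titration Period".
- Protocol 5.2: downward adjustment in Maintenance is available "if needed to manage non-hepatic side effects and may also be increased back"; liver-related discontinuation is referred to Section 7.3.7.
- SAP 3.3.2: the same non-hepatic limit, followed by "Temporary or permanent study drug discontinuation for management of abnormal liver chemistry test results is allowed".

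**The concern.** The severe levels restrict what may happen after the drug has been stopped, but nothing in the text stops it. A subject managed by dose reduction has nothing to resume, so the bar does not reach that subject. The written rule is therefore stricter for restarting than for never stopping.

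This matters because subjects are enrolled on the strength of earlier liver injury attributed to tolvaptan. Protocol 3.2 treats them as being at higher risk. Protocol 1.7 reports liver failure leading to transplantation with tolvaptan and describes stopping that drug on elevated tests as the way serious outcomes are prevented. One of the three levels is a combined transaminase and bilirubin elevation, which the plan itself singles out for eDISH display.

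A secondary point concerns the endpoints. The primary endpoint and the >5 x ULN secondary both require that the event led to discontinuation, so the choice between reduction and interruption partly decides where an attributed event is counted.

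**Working it through.** The plan states no figure to reproduce. The check is a reading of each dosing rule against the others, with one piece of arithmetic.

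**1. What 7.3.7.2 requires at each level**

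| Level | Required action | Is a stop required? |
|---|---|---|
| Transaminase >3 x ULN or bilirubin >2 x ULN | Reduction or interruption | No; either satisfies the rule |
| Transaminase >8 x ULN | As above; no resumption unless the exception applies | No |
| Transaminase >5 x ULN for more than 2 weeks | As above; no resumption unless the exception applies | No |
| Transaminase >3 x ULN with bilirubin >2 x ULN | As above; no resumption unless the exception applies | No |

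**2. Whether another section supplies the stop**

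- 4.2.7 makes discontinuation advisable in some cases and keeps reduction open in others. It also asks for discussion with the medical monitor and sponsor before any action, except in an emergency.
- 4.2.4 leaves withdrawal for an adverse event to the Investigator's opinion and gives no liver threshold.
- 5.2 and the visit sections (6.3.1, 6.3.2, 6.4.1, 6.4.2) send liver cases to 7.3.7.
- SAP 3.3.2 allows discontinuation but does not require it.

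None does. The synopsis and 7.3.7.2 allow reduction for hepatic reasons, while 5.2 and SAP 3.3.2 confine downward adjustment in Maintenance to non-hepatic effects. The dosing sections therefore do not settle whether hepatic reduction is available at all.

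**3. Conditions attached to further dosing after a severe level**

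| Step | HERC likelihood of 50% or less | Agreed intensive plan | Specific consent |
|---|---|---|---|
| Resume after interruption | Yes | Yes | Yes |
| Continue on a reduced dose | No | No | No |
| Return to the titration dose after reduction | No | No | No |

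One of these three steps carries the conditions. If re-escalation is treated as a continuation of the reduction route, it is one of two.

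**4. How small a compliant reduction can be** (dose levels from Protocol Table 4)

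- Level 4: 200 + 200 = 400 mg/day.
- Level 4a: 200 + 150 = 350 mg/day; (400 - 350)/400 = 12.5%.
- Level 2: 100 + 100 = 200 mg/day; (400 - 200)/400 = 50%.

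Because 7.3.7.2 gives no size, either reduction complies.

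**5. Where a severe, attributed event managed by reduction would be counted**

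- Not in the primary endpoint (2.2.1) or the >5 x ULN secondary (2.2.2), since both require discontinuation.
- In the dose-reduction secondary if ALT exceeds 3 x ULN, and in the planned additional hepatic tables and eDISH plots (Protocol 8.4.3, SAP 8.6.3), the AESI tables and the listings.

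**The case against.** The strongest reply is that the wording presupposes a stop. Barring resumption and speaking of re-challenge make sense only if dosing has ceased. Section 5.2 says that permanent discontinuation for liver tests is described in 7.3.7, and the severe levels are the only content there that could correspond to it. Section 4.2.7 likewise speaks of restarting. On this view the fault is a missing sentence, and exploiting it would need the Investigator, medical monitor and sponsor to choose, after consultation, a reading the vocabulary resists. Oversight also applies on every route: HERC review, retesting within 48 hours, at least weekly testing in the first month while values stay elevated, and a 24-hour AESI report. Level 4a was designed for aquaretic intolerance, so the 12.5% cut is hypothetical. Re-escalation is arguably a later step on the reduction route.

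Much of this stands. A stop was probably intended, the oversight is real, and the route count and the 12.5% figure are illustrations on which the point does not depend. But probable intent is not an instruction to a site, and 4.2.7 and the synopsis expressly keep hepatic reduction open. The listed safeguards detect and review an event; none of them ends dosing.

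**Conclusion.** The concern holds. Neither document requires study drug to be stopped at any of the three severe levels, and dose reduction is available above 3 x ULN with no upper limit and no stated size. The consequence is mainly one of patient safety: the HERC limit, monitoring plan and consent can be bypassed by never interrupting. Events would not be hidden, since they remain visible in other planned outputs.

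The conclusion rests on a literal reading of the rule. It does not assume that any site would act on that reading. The documents give no frequency for severe elevations, so no effect on the primary proportion can be stated. SAP Section 9 reports early termination with only 6 participants entering maintenance. That lowers the urgency for this trial but does not correct the rule for any further dosing or reuse of the text. It should be fixed.

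**What to change.** In Protocol 7.3.7.2, state that study drug must be interrupted at any of the three severe levels and that dose reduction is available only below them. State that any further dosing after a severe level, whether continuing, re-escalating or resuming, requires the same HERC verdict, agreed intensive monitoring plan and specific consent.

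Carry this into 4.2.7, 5.2 and the synopsis, and make 5.2 and the synopsis agree on whether hepatic dose reduction is allowed below the severe levels. Use one HERC cut-off: 7.3.7.2 accepts 50% or less, whereas 4.2.7 requires less than 50%.

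The cost is protocol wording in four places, with no new visits, tests or patients. The Investigator and medical monitor lose a little case-by-case discretion.

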2.2 Study Endpoints

2.2.1 Primary Endpoint

Safety:

- Proportion of subjects who develop ALT levels >3 x ULN during the Titration or Maintenance Periods that were assessed by the independent Hepatic Events Review Committee (HERC) to be at least probably related to lixivaptan and resulted in discontinuation of the study drug.

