2.2.2 Secondary Endpoints

Safety:

- Proportion of subjects who develop ALT levels >5 x ULN during the Titration or Maintenance Periods that were assessed by the independent HERC to be at least probably related to lixivaptan and resulted in discontinuation of the study drug.
- Proportion of subjects who develop ALT levels >3 x ULN during the Titration or Maintenance Periods that were assessed by the independent HERC to be at least probably related to lixivaptan and resulted in dose reduction of the study drug.

- The safety and tolerability of lixivaptan assessed through evaluation of AEs, clinical laboratory findings (clinical chemistry including additional analyses of liver chemistry tests, hematology and urinalysis), vital signs, and 12-lead electrocardiograms (ECG).

Efficacy:

- Change in eGFR from baseline (mean of 3 eGFR determinations obtained during Screening and Baseline Periods) to final assessment (mean of 3 eGFR determinations obtained during the Follow-up Period).

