4.2.4 Reasons for Withdrawal

Reasons for withdrawal (subjects who refuse to return for any remaining study visits) or discontinuation (subjects who prematurely stop the treatment) at any time during the study may include, but are not limited, to the following:

1. No longer meet the protocol inclusion or exclusion criteria, e.g., require a prohibited concomitant medication.
2. Noncompliance with the protocol.
3. Lack of efficacy.
4. A serious or intolerable AE that, in the Investigator's opinion, requires withdrawal from the study, including but not limited to laboratory safety assessments that reveal clinically significant (CS) hematological or biochemical changes from the baseline values, other than changes that are expected for vasopressin antagonists, and symptoms of an intercurrent illness that justifies withdrawal. If the AE is related to abnormal liver chemistry test results, see [Section 7.3.7](#) for additional follow-up requirements. Mild elevations in serum creatinine or serum sodium are known pharmacodynamic effects of vasopressin antagonists like lixivaptan and are transient and reversible. Therefore, subjects should not be withdrawn from study participation solely due to mildly elevated serum creatinine or serum sodium. Cases where eGFR has declined by 25% or more from baseline should be discussed with the medical monitor and sponsor.
5. Death
6. Lost to follow-up.
7. Other (e.g., pregnancy, study burden, development of contraindication to use of study drug).
8. Withdrawal of consent (partial or complete).
9. Investigator's or Sponsor's decision to discontinue the subject's participation in the study.
10. Sponsor termination of the study.

Upon occurrence of an SAE or intolerable AE, the Investigator will confer with the medical monitor and Sponsor. If a subject is discontinued from study drug because of an AE, the

event will be followed until it is resolved or stable or up to 28 days as determined by the Investigator. Any subject may withdraw his or her consent at any time. Subjects' safety will be closely monitored throughout the study, and the study will be conducted following Good Clinical Practices (GCP). The entire study may be stopped at any time at the discretion of the Sponsor.

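### A probably related ALT >3 x ULN that is interrupted and restarted at the same dose is named in no adjudicated hepatic endpoint

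*Protocol*

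**What the plan says.** **Required action.** Under Protocol 7.3.7.2, once transaminases exceed 3 x ULN or total bilirubin exceeds 2 x ULN in Titration or Maintenance, "temporary reduction in dose or interruption of study drug administration must be instituted" after consultation with the medical monitor and sponsor. No dose level is named. The section goes on: "In the case of study drug interruption, re-starting study drug should be encouraged".

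**Limits on restart.** "Treatment with study drug cannot be resumed in subjects when" transaminases exceed 8 x ULN at any time, exceed 5 x ULN for more than 2 weeks, or exceed 3 x ULN together with bilirubin above 2 x ULN. The exception is an event that the HERC rates as no more than 50% likely to be related.

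**Endpoints.** The primary endpoint (2.2.1) counts ALT >3 x ULN judged "at least probably related to lixivaptan and resulted in discontinuation of the study drug". The second secondary endpoint (2.2.2) counts ALT >3 x ULN judged "to be at least probably related to lixivaptan and resulted in dose reduction of the study drug". The first secondary endpoint is the >5 x ULN version of the primary. The synopsis, Protocol 8.4.1 and 8.4.2, and SAP 4.1, 4.2.1, 8.6.1 and 8.6.2 name the same two actions.

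**Terms.** Protocol 4.2.4 describes discontinuation as stopping treatment prematurely. SAP 8.6.5 puts reduced and interrupted doses in one row and study drug withdrawal in another. Other places are looser. Protocol 4.2.7 says "If study drug is withdrawn, re-starting study drug should generally be encouraged". Protocol 5.2 says "Temporary or permanent study drug discontinuation for management of abnormal liver chemistry test results is described further in" Section 7.3.7. Appendix 4 and SAP 3.3.2 also speak of discontinuation that may be temporary or permanent.

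**The concern.** The protocol prescribes two responses to an ALT above 3 x ULN, and the adjudicated endpoints name only one of them, plus permanent stopping. Take two subjects with the same probably related elevation. If the first has the dose cut, that subject enters the second secondary endpoint. If the second is held and restarted at the same dose, that subject enters none.

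The HERC decides causality independently. It does not decide the action, which is agreed case by case with the medical monitor and sponsor in an open-label study. So the headline proportions for the primary objective depend partly on a management choice, and they can read zero when the HERC has found a related event.

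**Working it through.** The plan gives no figure to reproduce here. The sample size of up to 50 rests on a precedent study (Protocol 8.1, SAP section 5), with no assumed event rate. The check sets the action rule beside the endpoint wording and then sizes the effect of one case.

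**Step 1. Follow each path for a probably related ALT >3 x ULN.**

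| Management | Primary | Second secondary |
|---|---|---|
| Stopped permanently | counted | not counted |
| Dose reduced, drug continued | not counted | counted |
| Interrupted, restarted at a lower dose | not counted | can be counted as dose reduction |
| Interrupted, restarted at the same dose | not named | not named |

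Only the last row is a gap. The interruption option is not tied to a dose, so it can arise at any level.

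**Step 2. Bound the gap by severity.** Below the three limits in 7.3.7.2, restart does not depend on the HERC rating, so a related case may resume. Above them, a related case cannot resume and becomes a discontinuation. There is one small overlap: a rating of exactly 50% is probable in Appendix 2 and still permits re-challenge. Apart from that, the gap is ALT >3 to 8 x ULN, not >5 x ULN for more than 2 weeks, and without bilirubin >2 x ULN. Within it, a peak above 5 x ULN also misses the first secondary endpoint, which counts discontinuation only.

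**Step 3. Size it.** The SAP specifies exact binomial 95% intervals (8.6.1, 8.6.2). For x events in n subjects, the lower limit is the 0.025 quantile of Beta(x, n − x + 1), or 0 when x = 0. The upper limit is the 0.975 quantile of Beta(x + 1, n − x). For x = 0 the upper limit reduces to 1 − 0.025^(1/n); at n = 50 this is 1 − 0.025^0.02 = 7.11%. Each uncounted subject moves the proportion by 1/n.

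| n | As worded | Assumed cases | If interruption counts |
|---|---|---|---|
| 50 (planned) | 0/50: 0 to 7.11% | 1 | 2.0% (0.05 to 10.65%) |
| 50 (planned) | 0/50: 0 to 7.11% | 3 | 6.0% (1.25 to 16.55%) |
| 10 (assumed) | 0/10: 0 to 30.85% | 1 | 10.0% (0.25 to 44.50%) |
| 6 (entered Maintenance) | 0/6: 0 to 45.93% | 1 | 16.7% (0.42 to 64.12%) |

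The documents report no such subject, so every case count is an assumption. SAP section 9 gives 6 participants in Maintenance. The Safety Population is not stated but must be at least 6, so 16.7 points is the largest shift that one subject can cause. The n = 6 and n = 10 rows are illustrations of scale, because SAP section 9 says no statistical analyses will be performed.

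**The case against.** The best defence is that the endpoints grade related events by consequence and that other outputs catch the rest. This is largely true. All ALT elevations above 3 x ULN were to be tabulated regardless of cause or action (Protocol 8.4.3, SAP 8.6.3), every one goes to the HERC, and HERC judgements are listed. SAP 8.6.5 summarises liver events as AESIs and groups reduced with interrupted doses. A reader might infer that related events are hidden; the documents do not support that. What stands is narrower: the adjudicated proportions themselves are incomplete. Appendix IV keeps a table and a listing for those endpoints (Table 14.3.2.1 and Listing 16.2.7.2), but no table titled for the all-cause ALT proportions.

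A reader might also infer that every interrupted and restarted subject drops out. That is too strong, because the synopsis allows dose reduction for hepatic events and a restart at a lower dose can count as one. Nor is this a problem of Level 2 in particular. If anything Level 1 is sharper, since no lower level is listed. The note limiting Level 1 to initiation sits under a titration table, and neither it nor the 100 mg BID entry minimum clearly bars a temporary reduction to 50 mg BID.

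Finally, one might argue that a temporary stop belongs in the primary endpoint. The loose wording in Protocol 5.2, Appendix 4 and SAP 3.3.2 leaves some doubt, but 4.2.4 and SAP 8.6.5 favour reading discontinuation as permanent. With so few subjects, a restarted case can be read from the listings, so the practical effect on this terminated study is small.

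**Conclusion.** The concern holds in a limited form. One of the two responses required by 7.3.7.2, when followed by restart at the same dose, is missing from the adjudicated endpoints, and neither document classifies it. The effect is 2.0 percentage points per subject at n = 50 and at most 16.7 points if the Safety Population is as small as 6. This rests on an assumed number of such subjects and on discontinuation meaning permanent stopping. If temporary stops were counted as discontinuation, the same shift would fall on the primary endpoint instead.

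More severe related events are outside the gap, and no event is lost from the record. It should still be corrected, because it concerns the headline related-event counts and Appendix IV still reports them.

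**What to change.** 1. Widen the action in the second secondary endpoint to *dose reduction or temporary interruption of the study drug*. Change it in the synopsis, Protocol 2.2.2 and 8.4.2, and SAP 4.2.1 and 8.6.2, and apply it in Table 14.3.2.1 and Listing 16.2.7.2.
2. State that discontinuation, in the primary and first secondary endpoints, means a recorded decision to stop study drug permanently because of the liver event. A hold still open when treatment ends for another reason (end of Maintenance, withdrawal, sponsor termination) is an interruption. A subject with both an interruption and a discontinuation counts in the discontinuation endpoint only.

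The decision rule in item 2 is safer than one based on whether drug was restarted by the last visit. Such a rule would turn a temporary hold cut short by study termination into a primary event, and SAP section 9 says most Maintenance participants were prematurely terminated.

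**Cost.** No new data or visits are needed. Interruption dates are already recorded (Protocol 5.6), causes of premature discontinuation are documented (4.2.3), and SAP 8.6.5 already uses the combined grouping. No dosing option is removed. One descriptive secondary endpoint is redefined and its proportion may be higher. A change to the protocol text needs ethics approval before it is implemented (11.2.1). Applied after termination, it should be labelled a post hoc clarification in the table, the listing and the study report.
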